## **BACKGROUND AND RATIONALE**

Tinnitus is a common symptom of clinically heterogeneous pathologies and is defined as the conscious perception of an auditory sensation in the absence of a corresponding external stimulus. Tinnitus, in its debilitating form, negatively affects emotional health and social well-being, and can precipitate psychological distress severe enough to cause self-harm and suicidal ideations, while exerting substantial individual and societal financial burden. Therefore, it becomes crucial to take adequate preventive measures and health interventions. According to population-based studies from Western Europe and US, tinnitus prevalence lies between 10% and 15%. Nonetheless, there is a lack of clear understanding of global prevalence of tinnitus. Inherent methodological drawbacks and between study differences hinder deriving a global estimate by pooling data from studies conducted in different countries and world regions. Therefore, uncertainties with regards to the prevalence of tinnitus remain.

Being a subjective condition, the impact of tinnitus symptoms depends on its perceived bothersomeness or severity. Therefore, "bothersome" or "severe" tinnitus symptoms are a better predictor for the emotional, societal and financial burden of tinnitus than "any" tinnitus. The economic burden is directly related to the severity of the tinnitus symptoms, with increased healthcare costs in people with severe tinnitus. In a study conducted in the Netherlands, the mean annual costs per patient was €767 for mild, €1329 for moderate and €2218 for severe tinnitus. A similar pattern was noted in a study in USA, where medical costs were reported to be directly proportional to severity of tinnitus. While epidemiological studies have attempted to distinguish any and severe tinnitus, both these concepts are troubled by heterogeneous prevalence estimates. Hearing difficulty is a major risk factor for tinnitus and often co-occur in an individual. However, not many studies have measured the prevalence of tinnitus in a population with hearing difficulty.

## **OBJECTIVE**

The primary objective of this population-based cross-sectional study is to estimate the overall and country specific prevalence of any tinnitus, bothersome tinnitus, and severe tinnitus in 12 European Union (EU) countries.

The study data have been analyzed to fulfil the following secondary objectives:

- To examine inter-country differences in prevalence of tinnitus by making the following comparisons:
  - Comparing prevalence estimates in countries with relatively low versus high gross domestic product (GDP) per capita
  - Comparing prevalence estimates in countries within different European regions (i.e., Northern, Southern, Eastern and Western Europe)
- To understand the effect of sex, age, socio-economic variables, body mass index (BMI), and marital status on overall prevalence of tinnitus
- To assess the effect of hearing difficulty on tinnitus prevalence
- To explore the effect of tinnitus severity on use of healthcare resource for tinnitus

## METHODS

### Study design

To achieve the aims of this study, we conducted face-to-face population-based cross-sectional survey in 12 strategically selected EU28 countries (Bulgaria, England, France, Germany, Greece, Ireland, Italy, Latvia, Poland, Portugal, Romania, and Spain). The study methodology is similar to another Pan-European survey on second-hand smoking and e-cigarettes, the TackSHS Project (“Tackling secondhand tobacco smoke and e-cigarette emissions: exposure assessment, novel interventions, impact on lung diseases and economic burden in diverse European populations”; [www.tackshs.eu](http://www.tackshs.eu)) conducted in the same 12 countries in 2017-2018, funded by the European Commission (EC) within the Horizon 2020 research grants (grant agreement number: 681040).

For each country, the study sample is representative of the general population aged 18 years and above in terms of age, sex, geographic area, and socio-economic characteristics. Multi-stage methodology was used as the preferred sampling methodology. In the first stage, the primary unit of selection was geographic area or voting center. In the second stage, households or municipalities were selected. In the last stage, respondents were chosen randomly, in order to be representative of the population. Other methods, including stratified or simple sampling or quota methods, were also accepted wherever it is not possible to conduct a multistage random sampling.

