### Study population

In each of the 12 selected European countries, approximately 1000 individuals, representative of the general population aged 18 years and above in terms of age, sex, geographic area, and socio-economic characteristics, were enrolled in this cross-sectional study. The final sample therefore includes a total of 11,427 subjects.

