### Sample size computation

The sample size for each country allowed us to obtain prevalence estimates with a maximum standard error (SE) lower than  $\pm 1.6\%$ . Therefore, with such a sample size we have been able to provide stable prevalence estimates (with a relatively small 95% confidence interval), both overall and country-specific.

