#### Statistical analyses

Statistical analyses required to achieve objectives has been conducted by the teams from the Laboratory of Lifestyle Epidemiology, Department of Environmental Health Sciences of Mario Negri Institute and the University of Nottingham, using SAS statistical package. Prevalence of three working definitions of tinnitus (any, bothersome and severe tinnitus) have been estimated through univariate statistical analyses (i.e., descriptive statistics for categorical data, including absolute or relative frequencies), overall, by country, and in strata of selected demographic and socio-economic (individual and country-specific) characteristics. Continuous variables have been summarized through the use of means and standard deviations. Alternatively, they have been categorized, and thus described through absolute or relative frequencies.

Multivariate analyses have been conducted to identify sub-groups of the population (e.g., based age-groups, low vs. high educated subjects) or clusters of countries (e.g., based on income levels and regional groups) where tinnitus is more frequent. Thus, odds ratios (OR), and the corresponding 95% confidence intervals (CI), were estimated through logistic regression models after adjustment for selected individual-level characteristics.

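### The 1.6% per-country SE bound reproduces only as a simple-random-sample worst case at n = 1000, and the plan states no allowance for its multi-stage sampling in the prevalence CIs or odds ratios

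*Combined protocol and SAP*

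**What the plan says.** The primary objective is overall and country-specific prevalence of any, bothersome and severe tinnitus in 12 countries.

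- **Study design.** Multi-stage sampling is preferred. Areas or voting centers come first, and then "In the second stage, households or municipalities were selected. In the last stage, respondents were chosen randomly". Departures are allowed: "Other methods, including stratified or simple sampling or quota methods, were also accepted wherever it is not possible" to use the preferred method.
- **Sample size computation.** "The sample size for each country allowed us to obtain prevalence estimates with a maximum standard error (SE) lower than" ±1.6%. From this the section concludes that the survey gives "stable prevalence estimates (with a relatively small 95% confidence interval), both overall and country-specific". It states no prevalence, formula, design effect, intracluster correlation (ICC) or cluster size.
- **Study population.** The target is about 1000 per country. "The final sample therefore includes a total of 11,427 subjects". Numbers by country are not given.
- **Statistical analyses.** Prevalence is estimated by "univariate statistical analyses (i.e., descriptive statistics for categorical data, including absolute or relative frequencies"). The only interval named in this section is for regression: "odds ratios (OR), and the corresponding 95% confidence intervals (CI), were estimated through logistic regression models", adjusted for individual-level characteristics.

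No section mentions survey weights, cluster or stratum variables for variance estimation, robust variance or a design effect. The strata and country clusters in the Statistical analyses section are reporting groups, and stratified sampling in the Study design section is a fallback way to select respondents.

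**The concern.** People in the same area or household tend to resemble one another, so a multi-stage sample usually carries less information than a simple random sample of the same size. An interval that ignores this is too narrow whenever the net design effect exceeds 1. The primary results are country-specific prevalences, and the secondary objectives compare groups of countries, so understated uncertainty would bear on both. For quota samples, a design-based SE is not defined at all, and the plan does not say what an interval would mean there.

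The precision statement raises a second question. It appears to be built on simple random sampling and on the planned rather than the achieved sample, so it may describe neither the design used nor the data collected.

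**Working it through.** **Inputs.** From the documents: SE bound 1.6 points; planned n of about 1000 per country; achieved total 11,427 in 12 countries (mean 952.25); background prevalence 10-15%. Assumed, because the documents are silent: the maximum SE refers to p = 0.5 under simple random sampling.

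**1. Reproduce the plan's figure.** SE = √(p(1−p)/n). At p = 0.5 and n = 1000: √(0.25/1000) = 1.581 points, just under 1.6.

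**2. Room for a design effect.** 0.016² / (0.25/1000) = 1.024. The bound therefore contains almost no allowance for clustering.

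**3. Check against the achieved sample.**
- Required n: 0.25/0.016² = 976.6, so 977 per country, and 12 × 977 = 11,724.
- Shortfall: 11,724 − 11,427 = 297. Not every country can have 977.
- Because the mean is 952.25, at least one country has 952 or fewer. Its worst-case SE is at least √(0.25/952) = 1.62 points.
- Up to 11 countries could still meet the bound if one had 11,427 − 11 × 977 = 680 or fewer. Which countries miss, and by how much, cannot be read from the documents.

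**4. Where the miss matters.** At n = 952 the simple-random-sample SE exceeds 1.6 only for p within 0.5 ± √(0.25 − 0.016² × 952), that is 42.1% to 57.9%. At p = 10% the SE is 0.97 points and at 15% it is 1.16. The design effect that would bring these to 1.6 is 0.016² × 952/0.09 = 2.71 at 10% and 0.016² × 952/0.1275 = 1.91 at 15%.

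**5. Illustration of what ignoring the design could cost.** Assume m = 10-20 interviews per sampling point, an ICC of 0.01-0.02, and no offset from stratification or quotas. None of these values comes from the documents.
- Design effect = 1 + (m − 1) × ICC: from 1 + 9 × 0.01 = 1.09 to 1 + 19 × 0.02 = 1.38.
- Coverage of a simple-random-sample 95% CI = 2Φ(1.96/√DEFF) − 1: from 94.0% to 90.5%.
- 95% half-width at n = 952:

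| Prevalence | DEFF 1 | DEFF 1.09 | DEFF 1.38 |
|---|---|---|---|
| 10% | 1.91 | 1.99 | 2.24 |
| 15% | 2.27 | 2.37 | 2.66 |

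No figure is claimed for the odds ratios.

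**The case against.** The strongest reply is that nothing here shows a wrong analysis. The plan writes down no prevalence CI method, so a naive binomial interval cannot be attributed to it, and an allowance may have been made without being recorded. This stands: the documents show an omission, and the coverage figures describe only what would follow if simple-random-sample intervals were used.

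The 1.6 bound can also be defended. The sample size section gives neither p nor formula, the sample was described as approximate, and 1.62 rounds to 1.6. A design slightly more efficient than simple random sampling (design effect about 0.975 or less at the mean n) would meet the bound, and stratified sampling was permitted. A reader might infer that the bound flatly fails in some country. The documents support that only on the p = 0.5, simple-random-sample reading. That is the reading that reproduces the figure, but it remains an inference, and no more efficient design is documented.

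Finally, the illustration has no anchor in the documents. Multi-stage sampling was preferred, not universal; the number of countries using it is unknown; stratification or quota balance may offset clustering. A more extreme choice (ICC 0.05 with 20 interviews per point, design effect 1.95) would give 84.0% coverage, but that is one corner of an assumed range and should not be read as an estimate. None of these points supplies the missing CI method.

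**Conclusion.** The point holds in a limited form.

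- **Precision statement.** It has no stated basis, reproduces as a simple-random-sample worst case at the planned n, and on that basis is not met in at least one country at the achieved n. The miss starts at 0.02 points (1.62 against 1.60) and has no consequence at 10-15% prevalence under simple random sampling. It is a figure to restate.
- **Interval method.** This is the weightier part. The primary results need an interval, the preferred design is multi-stage, and no design-based variance is specified for prevalence or for the regression. The direction is clear wherever the net design effect exceeds 1; the size cannot be computed. In the illustrative range, half-widths at 10-15% prevalence grow by less than 0.4 points.

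A reader might infer that the sample is too small or that reported intervals are invalid. The documents support neither: at the background prevalence the 1.6 bound survives design effects up to 1.91-2.71, and what the actual analysis did is not shown. This should be corrected, with medium confidence about its practical size.

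**What to change.** 1. **Restate the SE** from each country's achieved n. Either label it a simple-random-sample worst case or add a stated design effect.
2. **State the prevalence CI method.** Where sampling-point, stratum or weight fields are in the 12 delivered data files, use PROC SURVEYFREQ. Where they are not, report the simple-random-sample CI with a labelled design-effect range as a sensitivity analysis.
3. **Quota-sampled countries:** label the CI as model-based. According to the Data collection section, the sampling method is already supplied for each country.
4. **Pooled odds-ratio models:** use PROC SURVEYLOGISTIC with country as stratum and sampling point as cluster where available. Treat respondents in countries without codes as their own clusters, and state that limitation, since clustering in those countries stays unaccounted for.

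**Cost.** SAP wording, a check of the files and codebook for design fields, and a re-run in the SAS package already in use. The documents do not say whether those fields were delivered. The privacy section says that the encryption key was destroyed and identifiers deleted after quality assurance, so later linkage of missing sampling-point codes may be impossible; hence the fallback in step 2. The downside is somewhat wider intervals and a slightly less favourable stated precision. Prevalence estimates themselves change only if a supplied weight is applied.

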### Selection of countries

For the present study, an appropriate sample of 12 European countries—all EU28 Member States (MS)—representing geographical, legislative and cultural variations across the EU, have been selected. The selected European countries are as follows: Bulgaria (BG), England (UK), France (FR), Germany (DE), Greece (GR), Ireland (IE), Italy (IT), Latvia (LV), Poland (PL), Portugal (PT), Romania (RO), and Spain (ES). These countries were selected after taking into account several aspects, including: i) different geographical distribution; ii) different level of per capita income. According to geographic area, we considered countries from northern (IE, UK), central/western (DE, FR), central/eastern (BG, LV, PL, RO), and southern Europe (ES, IT, GR, PT). Moreover, the selection includes the 7 most populated EU28 MS (DE, ES, FR, IT, UK, PL, RO), and, among less populated countries, we prioritized middle-income countries (BG, RO). Overall, the 12 selected EU MS represent 78.8% of the EU28 overall population.

### Study population

In each of the 12 selected European countries, approximately 1000 individuals, representative of the general population aged 18 years and above in terms of age, sex, geographic area, and socio-economic characteristics, were enrolled in this cross-sectional study. The final sample therefore includes a total of 11,427 subjects.

### Inclusion criteria

- individuals aged 18 years and above
- individuals who are residents of the 12 selected countries
- individuals able to understand and answer the questions of the study questionnaire in the country-specific language
- individuals who formally accept to participate in the study

### Exclusion criteria

No specific exclusion criteria are considered

### Sample size computation

The sample size for each country allowed us to obtain prevalence estimates with a maximum standard error (SE) lower than  $\pm 1.6\%$ . Therefore, with such a sample size we have been able to provide stable prevalence estimates (with a relatively small 95% confidence interval), both overall and country-specific.

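### The per-country maximum SE below 1.6% fits a nominal 1000 respondents per country; the achieved 11,427 cannot meet it in every country at p = 0.5, and the sampling design is not allowed for

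*Combined protocol and SAP*

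**What the plan says.** The precision statement is in Sample size computation: "The sample size for each country allowed us to obtain prevalence estimates with a maximum standard error (SE) lower than" ±1.6%. From this the section concludes that "we have been able to provide stable prevalence estimates (with a relatively small 95% confidence interval), both overall and country-specific". It shows no sample size, assumed prevalence, formula or design effect.

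The sample itself is described under Study population. Each country was to contribute "approximately 1000 individuals, representative of the general population aged 18 years and above", and then: "The final sample therefore includes a total of 11,427 subjects". The sizes of the individual country samples are not given.

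On selection, Study design says: "Multi-stage methodology was used as the preferred sampling methodology". It adds: "Other methods, including stratified or simple sampling or quota methods, were also accepted wherever it is not possible to conduct a multistage random sampling".

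The primary objective is "to estimate the overall and country specific prevalence of any tinnitus, bothersome tinnitus, and severe tinnitus", so precision by country is part of the main purpose of the study.

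**The concern.** The bound is worded strictly, applies to each country and describes what the sample delivered. Two things in the same document sit badly with it. The final total is 573 short of 12 × 1000, so a figure that only just holds at 1000 may fail at the sizes obtained. And a formula that treats respondents as a simple random sample may not describe data collected by multi-stage or quota methods.

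This bound is the only quantitative support offered for the country-specific part of the primary objective. If it rests on a nominal sample and an unstated sampling assumption, a reader cannot tell how precise the country estimates are, or how far that depends on how each country was sampled.

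**Working it through.** **Inputs.** Bound of 1.6% per country (Sample size computation); about 1000 per country and 11,427 in total (Study population); 12 countries and the sampling methods (Study design); prevalence of 10-15% (Background and rationale). The document does not state p. I take p = 0.5, because the SE of a proportion is largest there and the text speaks of a maximum.

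**Formula.** SE = √(D·p(1−p)/n), where D is the design effect and D = 1 under simple random sampling.

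**1. Reproducing the stated figure.** With n = 1000, p = 0.5 and D = 1: √(0.25/1000) = 1.58%, which is below 1.6%.

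**2. Sample size that the bound needs.** 0.25/0.016² = 976.6, so n ≥ 977 per country. Over 12 countries, 12 × 977 = 11,724. The achieved total is 11,724 − 11,427 = 297 short.

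**3. Achieved sample.** 11,427/12 = 952.25. However the total is divided, at least one country has 952 or fewer. At n = 952, √(0.25/952) = 1.62%, with a 95% half-width of 1.96 × 1.62 = 3.2 points.

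**4. Range of p in which the bound fails at n = 952, D = 1.** This requires p(1−p) > 0.016² × 952 = 0.2437, that is, p between about 0.42 and 0.58.

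**5. At the cited prevalence, n = 952, D = 1.**

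| p | SE | 95% half-width | Design effect at which SE reaches 1.6% |
|---|---|---|---|
| 10% | √(0.09/952) = 0.97% | 1.9 points | 0.2437/0.09 = 2.7 |
| 15% | √(0.1275/952) = 1.16% | 2.3 points | 0.2437/0.1275 = 1.9 |

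**6. Pooled sample, unweighted, D = 1.** √(0.25/11,427) = 0.47%.

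**7. Room for a design effect at the nominal size.** At n = 1000 and p = 0.5 the bound fails once D exceeds 0.016² × 1000/0.25 = 1.024.

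**8. Illustration with assumed design effects, n = 952, p = 0.5.** The document gives no design effect; these values are assumptions.

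| Assumed D | SE |
|---|---|
| 1.0 | 1.62% |
| 1.5 | √(0.375/952) = 1.98% |
| 2.0 | √(0.5/952) = 2.29% |

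**The case against.** The strongest reply is that the miss depends on a prevalence the document never states, and that no country is likely to have tinnitus prevalence between 42% and 58%. At 10-15% the SE under simple random sampling is well inside the bound. That stands as a limit on the practical effect. It does not rescue the statement, because a maximum SE is by definition a worst case over p, and p = 0.5 is what reproduces the figure.

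Secondly, 1.62% rounds to 1.6%, and the 95% half-width moves only from 3.10 points at n = 1000 to 3.18 at the achieved mean. This is true, and the qualitative conclusion about stable estimates is not overturned by it. But the claim is a strict inequality, and rounding does not answer the point about sampling design.

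Thirdly, a section on sample size would ordinarily quote a planning figure, and the whole document is in the past tense, so tense alone proves little. That is fair. If the figure is nominal, the text should say so and should not present it as the precision obtained in each country.

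Fourthly, only one country is forced below 977. Eleven could have 977, leaving 11,427 − 11 × 977 = 680 for the twelfth. This is correct, but in that split the twelfth country would have √(0.25/680) = 1.92%, so concentrating the shortfall enlarges the miss there.

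Finally, no design effect is documented, and stratification can reduce variance. That stands: the size, and even the direction, may differ by country. The gap is that the bound assumes no effect without saying so. For a quota sample, a random-sampling SE has no basis in the design at all.

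**Conclusion.** The concern holds. Read at p = 0.5, the stated bound belongs to 1000 respondents per country under simple random sampling, and the achieved sample cannot meet it in all 12 countries. This conclusion does not need the unreported country sizes. Which countries miss the bound, and how many, cannot be determined.

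The demonstrated numerical failure is slight and confined to country-specific estimates. It gives no reason to think enrolment was inadequate. The larger uncertainty is the sampling design, whose effect cannot be derived from the document. At the cited prevalence and n = 952 it would take a design effect of roughly 2 to 3 to breach 1.6%, but at the worst case almost any inflation does so.

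**What to change.** Rewrite Sample size computation from the achieved country samples, stating p = 0.5 and the sampling assumption. For example: *Country samples ranged from [min] to [max]. At p = 0.5 under simple random sampling the maximum SE is 1.62% at the mean of 952 per country, and larger in smaller countries; this does not allow for clustering.* Drop the ± sign, which invites confusion with a confidence-interval half-width, and label the figure as an SE or as a 95% half-width.

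Where cluster and stratum identifiers are held, report design-based SEs and 95% confidence intervals for country prevalence. Otherwise show a range of design effects marked as assumed, and say which sampling method each country used so that the range can be interpreted.

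The cost is wording plus the achieved n by country. Data collection says the fieldwork partners supplied the sampling method for each country but does not mention cluster or stratum identifiers, so design-based SEs are an added analysis only where these exist. The one drawback is a slightly less favourable stated maximum SE.
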